AE284	HYPERTENSION – PULMONARY MEAN PULMONARY ARTERY PRESSURE THAT IS GREATER THAN 25 MMHG AT REST AND/OR GREATER THAN 30 MMHG DURING EXERCISE CONFIRMED BY SWAN GANZ CATHETER OR DIAGNOSTIC PLACEMENT IN THE PULMONARY ARTERY BED AND CONDITION REQUIRES MEDICAL INTERVENTION TO RESOLVE OR TREAT THE CONDITION.
AE285	HYPOTENSION ABNORMALLY LOW BLOOD PRESSURE. FOR AN ADULT, HYPOTENSION IS DEFINED AS BLOOD PRESSURE LESS THAN 90/50 MMHG.

AE CODE LIST	
CODE	DEFINITION
AE.7	
CARDIOVASCULAR - MISC (CONTINUED)
 
AN ACUTE MYOCARDIAL INFARCTION IS EVIDENCED BY ANY OF THE FOLLOWING:
 
 1. A RISE AND FALL OF CARDIAC BIOMARKERS (PREFERABLY TROPONIN) WITH AT LEAST ONE OF THE VALUES IN THE ABNORMAL RANGE (CK \geq 5X ULN) TOGETHER WITH AT LEAST ONE OF THE FOLLOWING MANIFESTATIONS OF MYOCARDIAL ISCHEMIA: 
 A) ISCHEMIC SYMPTOMS; B) ECG CHANGES INDICATIVE OF NEW ISCHEMIA (NEW ST-T CHANGES, NEW LEFT BUNDLE BRANCH BLOCK, OR LOSS OF R WAVE VOLTAGE); C) DEVELOPMENT OF PATHOLOGICAL Q WAVES IN 2 OR MORE CONTIGUOUS LEADS IN THE ECG (OR EQUIVALENT FINDINGS FOR TRUE POSTERIOR MI); D. IMAGING EVIDENCE OF NEW LOSS OF VIABLE MYOCARDIUM OR NEW REGIONAL WALL MOTION ABNORMALITY. 2. DEVELOPMENT OF NEW PATHOLOGICAL Q WAVES IN 2 OR MORE CONTIGUOUS LEADS IN THE ECG, WITH OR WITHOUT SYMPTOMS. 3. IMAGING EVIDENCE OF A REGION WITH NEW LOSS OF VIABLE MYOCARDIUM AT REST IN THE ABSENCE OF A NON-ISCHEMIC CAUSE. THIS CAN BE MANIFEST AS: A. ECHOCARDIOGRAPHIC, CT, MR, VENTRICULOGRAPHIC OR NUCLEAR IMAGING EVIDENCE OF LEFT VENTRICULAR THINNING OR SCARRING AND FAILURE TO CONTRACT APPROPRIATELY (I.E., HYPOKINESIS, AKINESIS, OR DYSKINESIS); OR, B. FIXED (NON-REVERSIBLE) PERFUSION DEFECTS ON NUCLEAR RADIOISOTOPE IMAGING (E.G., MIBI, THALLIUM).
AE286	MYOCARDIAL INFARCTION
AE287	MYOCARDITIS
AE296	PERFORATION - ATRIAL
AE297	PERFORATION - VENTRICULAR
AE289	PERFORATION - OTHER
AE290	PERICARDIAL EFFUSION - MAJOR
AE291	PERICARDIAL EFFUSION - MINOR
AE292	PERICARDIAL TAMPONADE - MAJOR
AE294	PERICARDITIS
AE295	CARDIOVASCULAR - OTHER

Clinical Investigational Plan
Protocol Number: 2010-03

AE CODE LIST	
CODE	DEFINITION
AE.8	GASTROINTESTINAL/HEPATIC
AE350	GASTROINTESTINAL – ESOPHAGEAL RUPTURE/TEAR ANY EVIDENCE OF PUNCTURE/DISSECTION/PERFORATION, VARICES OR OTHER DAMAGE TO THE ESOPHAGUS REQUIRING INTERVENTION.
AE351	GASTROINTESTINAL – INFECTION SEVERE INFLAMMATION OF THE GASTROINTESTINAL TRACT INVOLVING BOTH THE STOMACH AND SMALL INTESTINE RESULTING IN ACUTE DIARRHEA AND VOMITING. SHOULD BE CONFIRMED BY CULTURE
AE352	GASTROINTESTINAL – OTHER OTHER GASTROINTESTINAL EVENT THAT DOES NOT FIT IN ONE OF THE OTHER GI/HEPATIC CATEGORIES.
AE353	LIVER FAILURE - ACUTE A SYNDROME DEFINED BY THE OCCURRENCE OF ENCEPHALOPATHY, COAGULOPATHY AND JAUNDICE IN AN INDIVIDUAL WITH A PREVIOUSLY NORMAL LIVER.
AE354	LIVER FAILURE - CHRONIC CHRONIC LIVER DISEASE CAUSES CAN BE ANY CONDITION THAT RESULTS IN THE GRADUAL DEGRADATION AND RENEWAL OF THE TISSUE CELLS WITH A BODY'S LIVER. THIS PROCESS USUALLY RESULTS IN FIBROSIS OR CIRRHOSIS. DIAGNOSIS MAY BE CONFIRMED BY ABNORMAL BLOOD ENZYMES AND/OR BIOPSY
AE355	HEPATIC COMPLICATION - OTHER OTHER LIVER EVENTS THAT DO NOT MEET THE DEFINITION OF LIVER FAILURE (E.G. LIVER DYSFUNCTION) REQUIRING HOSPITALIZATION OR MEDICAL INTERVENTION.
AE356	PANCREATIC COMPLICATION (PANCREAS) AN EVENT PERTAINING TO, CONNECTED WITH, OR AFFECTING THE PANCREAS REQUIRING HOSPITALIZATION OR MEDICAL INTERVENTION.
AE357	SPLENIC COMPLICATION (SPLEEN) AN EVENT PERTAINING TO, CONNECTED WITH, OR AFFECTING THE SPLEEN REQUIRING HOSPITALIZATION OR MEDICAL INTERVENTION.
AE358	BILIARY (GALLBLADDER) AN EVENT PERTAINING TO BILE OR TO THE GALLBLADDER AND BILE DUCTS, WHICH TRANSPORT BILE REQUIRING HOSPITALIZATION OR MEDICAL INTERVENTION.
AE359	ENDOCRINE COMPLICATIONS AN EVENT PERTAINING TO, CONNECTED WITH, OR AFFECTING THE ENDOCRINE SYSTEM REQUIRING HOSPITALIZATION OR MEDICAL INTERVENTION.
AE360	METABOLIC COMPLICATIONS AN EVENT PERTAINING TO, CONNECTED WITH, OR AFFECTING THE METABOLIC SYSTEM REQUIRING HOSPITALIZATION OR MEDICAL INTERVENTION.
AE.9	GENITOURINARY/RENAL
AE370	URINARY TRACT INFECTION (UTI) INFECTION THAT AFFECTS ANY PART OF THE URINARY TRACT THAT REQUIRE HOSPITALIZATION OR MEDICAL INTERVENTION.
AE371	VAGINAL INFECTION INFECTIONS AFFECTING THE VAGINAL AREA THAT REQUIRE HOSPITALIZATION OR MEDICAL INTERVENTION.
AE372	GENITOURINARY – OTHER OTHER GENITOURINARY EVENT NOT PREVIOUSLY DESCRIBED REQUIRING HOSPITALIZATION OR MEDICAL INTERVENTION.
AE373	RENAL DYSFUNCTION AN ACUTE EVENT OR WORSENING OF RENAL FUNCTION POST-OPERATIVELY (INCREASE OF SERUM CREATININE TO < 2.0 , AND < 2X MOST RECENT PREOPERATIVE CREATININE LEVEL) AND DOES NOT REQUIRE DIALYSIS.

Clinical Investigational Plan
Protocol Number: 2010-03

AE CODE LIST	
CODE	DEFINITION

AE CODE LIST	
CODE	DEFINITION
AE.9	GENITOURINARY/RENAL (CONTINUED)
AE374	RENAL FAILURE – ACUTE AN ACUTE EVENT OR WORSENING OF RENAL FUNCTION RESULTING IN ONE OR MORE OF THE FOLLOWING: 1) INCREASE OF SERUM CREATININE TO >2.0, AND 2X MOST RECENT PREOPERATIVE CREATININE LEVEL. 2) A NEW REQUIREMENT FOR DIALYSIS POSTOPERATIVELY.
AE375	RENAL FAILURE – CHRONIC A PROGRESSIVE LOSS IN RENAL FUNCTION OVER A PERIOD OF MONTHS OR YEARS RESULTING IN A DIAGNOSIS OF STAGE 5 - CHRONIC KIDNEY DISEASE.
AE376	RENAL – OTHER OTHER EVENT THAT IS NOT RENAL FAILURE OR RENAL DYSFUNCTION THAT REQUIRES HOSPITALIZATION OR MEDICAL INTERVENTION.
AE.10	PULMONARY/RESPIRATORY
AE380	ATELECTASIS COMPLETE OR PARTIAL COLLAPSE OF A PREVIOUSLY INFLATED LUNG; INABILITY OF LUNG TO FULLY EXPAND.
AE381	HYPOXEMIA DECREASED PARTIAL PRESSURE OF OXYGEN IN BLOOD SOMETIMES SPECIFICALLY AS LESS THAN 60 MMHG (8.0 KPA) OR CAUSING HEMOGLOBIN OXYGEN SATURATION OF LESS THAN 90%.
AE382	PLEURAL EFFUSION - RIGHT EXCESS ACCUMULATION OF FLUIDS, SOMETIMES BLOOD IN THE PLEURAL SPACE, WHICH IS COMMON AFTER CARDIAC SURGERY. REPORTABLE WHEN IT BECOMES SYMPTOMATIC AND REQUIRES FLUID TO BE INTERVENTIONALLY REMOVED.
AE383	PLEURAL EFFUSION - LEFT "
AE384	PLEURAL EFFUSION - BILATERAL "
AE385	PNEUMOTHORAX ACCUMULATION OF AIR OR GAS IN THE PLEURAL CAVITY, OCCURRING BECAUSE OF DISEASE OR INJURY AND REQUIRING SURGICAL INTERVENTION, HOSPITALIZATION OR MEDICAL INTERVENTION TO RESOLVE.
AE386	PULMONARY EDEMA AN ABNORMAL ACCUMULATION OF FLUID IN THE LUNGS REQUIRING HOSPITALIZATION OR MEDICAL INTERVENTION TO RESOLVE.
AE387	PULMONARY HYPERTENSION MEAN PULMONARY ARTERY PRESSURE THAT IS GREATER THAN 25 MMHG AT REST AND/OR GREATER THAN 30 MMHG DURING EXERCISE CONFIRMED BY SWAN GANZ CATHETER OR DIAGNOSTIC PLACEMENT IN THE PULMONARY ARTERY BED AND CONDITION REQUIRES HOSPITALIZATION OR MEDICAL INTERVENTION TO RESOLVE.
AE388	PULMONARY REGURGITATION THE BACKWARD FLOW OF BLOOD FROM THE PULMONARY ARTERY, THROUGH THE PULMONARY VALVE, AND INTO THE RIGHT VENTRICLE OF THE HEART DURING DIASTOLE.
AE389	PULMONARY EMBOLISM - RIGHT CLINICAL EVIDENCE OF NEW EMBOLISM WITH CONFIRMATION BY LUNG SCAN OR PULMONARY ANGIOGRAPHY.
AE390	PULMONARY EMBOLISM - LEFT "
AE391	PULMONARY EMBOLISM - BILATERAL "
AE392	PULMONARY/RESPIRATORY - OTHER OTHER RESPIRATORY EVENT THAT IS NOT RESPIRATORY FAILURE.
AE393	RESPIRATORY DYSFUNCTION/INSUFFICIENCY DETERIORATION OF SUBJECT'S RESPIRATORY EFFORTS LESS THAN 24 HRS AFTER COMPLETION OF THE INDEX PROCEDURE.

Clinical Investigational Plan
Protocol Number: 2010-03

AE CODE LIST	
CODE	DEFINITION

AE CODE LIST	
CODE	DEFINITION
AE.10	PULMONARY/RESPIRATORY
AE394	RESPIRATORY FAILURE -ASTHMA
AE395	RESPIRATORY FAILURE -EMPHYSEMA
AE396	RESPIRATORY FAILURE -COPD
AE397	RESPIRATORY FAILURE -PNEUMONIA
AE398	RESPIRATORY FAILURE -PNEUMOTHORAX
AE399	RESPIRATORY FAILURE -HEMOTHORAX
AE400	RESPIRATORY FAILURE - ARDS
AE401	RESPIRATORY FAILURE -OTHER
AE402	RESPIRATORY INFECTION – UPPER (URI)
AE403	RESPIRATORY INFECTION – PNEUMONIA
AE.11	PERIPHERAL VASCULAR
AE420	VASCULAR - ACCESS SITE COMPLICATION
AE421	VASCULAR - DEEP VEIN THROMBOSIS (DVT)
AE423	VASCULAR - OTHER
AE.12	PSYCHIATRIC
AE431	PSYCHIATRIC DISORDER
AE432	SUICIDE
AE433	TRANSIENT PSYCHOTIC SYNDROME

NEED FOR MECHANICAL VENTILATION REQUIRED GREATER THAN 24 HRS AFTER OF COMPLETION OF THE INDEX PROCEDURE (TIME 0 = WHEN THE SUBJECT LEAVES THE OR), OR NEED FOR RE-INTUBATION AND VENTILATOR SUPPORT OCCURRING ANY TIME WITHIN 30 DAY OF THE INDEX PROCEDURE WILL BE CONSIDERED RELATED TO THE INDEX PROCEDURE.

"

"

"

"

"

" ACUTE RESPIRATORY DISTRESS SYNDROME

"

THE ILLNESSES CAUSED BY AN ACUTE INFECTION WHICH INVOLVES THE UPPER RESPIRATORY TRACT: NOSE, SINUSES, PHARYNX OR LARYNX. THIS COMMONLY INCLUDES: TONSILLITIS, PHARYNGITIS, LARYNGITIS, SINUSITIS, OTITIS MEDIA, AND THE COMMON COLD.

LUNG INFECTION DOCUMENTED BY BLOOD STUDIES OR CHEST X-RAY, REQUIRING TREATMENT WITH ANTIBIOTICS, INHALATION THERAPY, INTUBATION OR SUCTIONING.

COMPLICATIONS OF BLEEDING OR INFECTION AT THE SITE OF CARDIOPULMONARY ACCESS AND OR PERCUTANEOUS CORONARY INTERVENTION OR DIAGNOSTICS THAT REQUIRE HOSPITALIZATION OR MEDICAL INTERVENTION.

FORMATION OF BLOOD CLOT (THROMBUS) IN THE LOWER EXTREMITIES (LEGS) CHARACTERIZED BY SWELLING, REDNESS, CLAUDICATION/PAIN IN AFFECTED LIMB. EVENT SHOULD BE CONFIRMED BY DOPPLER OR DUPLEX US STUDY, AND REQUIRES HOSPITALIZATION OR MEDICAL INTERVENTION TO RESOLVE.

OTHER VASCULAR COMPLICATIONS GENERALLY RELATED TO A DISEASE PROCESS AND NOT TRAUMA THAT REQUIRE HOSPITALIZATION OR MEDICAL INTERVENTION.

A PSYCHOLOGICAL OR BEHAVIORAL PATTERN GENERALLY ASSOCIATED WITH SUBJECTIVE DISTRESS OR DISABILITY THAT OCCURS IN AN INDIVIDUAL, AND WHICH IS NOT A PART OF NORMAL DEVELOPMENT OR CULTURE. SUCH A DISORDER MAY CONSIST OF A COMBINATION OF AFFECTIVE, BEHAVIORAL, COGNITIVE AND PERCEPTUAL COMPONENTS.

A PERSON WHO INTENTIONALLY TAKES HIS OR HER OWN LIFE.

A MENTAL STATE OFTEN DESCRIBED AS INVOLVING A "LOSS OF CONTACT WITH REALITY" THAT LASTS ONLY FOR A

AE CODE LIST	
CODE	DEFINITION
	SHORT TIME.
AE.12	PSYCHIATRIC (CONTINUED)
AE434	PSYCHIATRIC – OTHER
AE.13	MUSCULAR SKELETAL/ DERMATOLOGIC
AE450	STERNAL WOUND/THORACIC INFECTION
AE451	BONE FRACTURE/BREAK
AE452	WOUND INFECTION – OTHER
AE454	INFECTION/INFLAMMATION - OTHER
AE456	MUSCULAR SKELETAL / DERMATOLOGIC - OTHER
AE.14	NONSPECIFIC, UNKNOWN, OR OTHER BODY SYSTEM
AE470	ANAPHYLACTIC REACTION
AE471	ALLERGIC REACTION – MEDICATION RELATED
AE472	ALLERGIC REACTION – OTHER
AE473	CANCER – PROGRESSION OF UNDERLYING DISEASE
AE474	CANCER – NEWLY DIAGNOSED
AE475	HEARING DISORDER
AE476	MULTI-SYSTEM ORGAN FAILURE
AE477	SPEECH DISORDER
AE479	VISION DISORDER
AE480	FEVER - UNKNOWN ORIGIN

AE CODE LIST	
CODE	DEFINITION
AE481	NONSPECIFIC, UNKNOWN, OR OTHER BODY SYSTEM - OTHER COMPLICATION
AE.15	DEVICE DYSFUNCTION
AE500	SVD - STUDY VALVE WEAR
AE501	SVD - STUDY VALVE FRACTURE
AE502	SVD - STUDY VALVE POPPET ESCAPE
AE503	SVD - STUDY VALVE CALCIFICATION
AE504	SVD - STUDY VALVE LEAFLET TEAR
AE505	SVD - STUDY VALVE STENT CREEP
AE506	SVD - STUDY VALVE SUTURE LINE DISRUPTION
AE507	SVD - STRUCTURAL VALVE DETERIORATION, OTHER
AE525	SVD - ANNULAR FRAME DAMAGE
AE526	SVD - ANNULAR FRAME SEPARATION
AE527	SVD - STENT FRAME FRACTURE
AE528	SVD - STENT FRAME DEFORMATION
AE529	SVD - STENT FRAME SEPARATION
AE512	NSD - ENTRAPMENT BY PANNUS, TISSUE, OR SUTURE
AE164	NSD - PARAVALVULAR LEAK - +1
AE165	NSD - PARAVALVULAR LEAK - +2
AE166	NSD - PARAVALVULAR LEAK - +3
AE167	NSD - PARAVALVULAR LEAK - +4
AE176	NSD - STUDY VALVE STENOSIS - MILD

ANY COMPLICATION THAT CANNOT OTHERWISE BE CATEGORIZED REQUIRING HOSPITALIZATION OR MEDICAL INTERVENTION.

INCLUDES DYSFUNCTION OR DETERIORATION INVOLVING THE OPERATED VALVE (EXCLUSIVE OF INFECTION OR THROMBOSIS). THE TERM STRUCTURAL VALVE DETERIORATION REFERS TO CHANGES INTRINSIC TO THE VALVE SUCH AS: WEAR, FRACTURE, CALCIFICATION, LEAFLET TEAR, MANUFACTURED SUTURE LINE DISRUPTION

"

"

"

"

"

"

"

"

"

"

"

"

"

"

"

ANY ABNORMALITY NOT INTRINSIC TO THE VALVE (DO NOT DIRECTLY INVOLVE VALVE COMPONENTS) ITSELF THAT RESULTS IN STENOSIS OR REGURGITATION OF THE OPERATED VALVE OR HEMOLYSIS (EXCLUDES THROMBOSIS AND INFECTION). EXAMPLES INCLUDE: ENTRAPMENT BY PANNUS, TISSUE, OR SUTURE, PARAVALVULAR LEAK, INAPPROPRIATE SIZING, INAPPROPRIATE POSITIONING, REGURGITATION AS A RESULT OF TECHNICAL ERROR, STJ DILATION, DILATION OF THE VALVE ANNULUS, OBSTRUCTION OF THE CORONARY OSTIA BY THE STUDY VALVE.

LEAKAGE BETWEEN THE SEWING RING AND THE ANNULUS.

"

"

"

"

NSD "

Clinical Investigational Plan
 Protocol Number: 2010-03

AE CODE LIST		
CODE	LABEL/NAME	DEFINITION
AE177	NSD - STUDY VALVE STENOSIS - MODERATE	NSD "
AE178	NSD - STUDY VALVE STENOSIS - SEVERE	NSD "
AE121	NSD - PARAVALVULAR LEAK WITH HEMOLYSIS	NSD "
AE514	NSD - INAPPROPRIATE SIZING	NSD "
AE515	NSD - INAPPROPRIATE POSITIONING	NSD "
AE516	NSD - RESIDUAL LEAK OR OBSTRUCTION	NSD "
AE517	NSD - INTRAVASCULAR HEMOLYTIC ANEMIA	NSD " CLINICALLY IMPORTANT
AE518	NSD - DEVELOPMENT OF REGURGITATION	NSD " AS A RESULT OF TECHNICAL ERRORS
AE519	NSD - DILATATION OF THE SINOTUBULAR JUNCTION	NSD "
AE520	NSD - DILATION OF THE VALVE ANNULUS	NSD "
AE521	NSD - CORONARY OSTIAL OBSTRUCTION	NSD "
AE522	NSD - STUDY VALVE INSTABILITY	NSD "
AE523	NSD - STUDY VALVE MIGRATION	NSD "
AE524	NSD - LVOT DAMAGE	NSD "

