15.1 ADVERSE EVENT (CODES AND DEFINITIONS)

Clinical Investigational Plan
 Protocol Number: 2010-03

AE CODE LIST		
CODE	LABEL/NAME	DEFINITION
AE.1	BLOOD AND LYMPHATIC (INCLUDING ALL BLEEDING COMPLICATIONS)	
AE101	ANEMIA – NON-BLEEDING RELATED	A CONDITION IN WHICH RED BLOOD CELL COUNT AND/OR HEMOGLOBIN ARE LESS THAN NORMAL DUE TO LACK OF PRODUCTION OF RED BLOOD CELLS, AND THAT REQUIRES TREATMENT OR TRANSFUSION.
AE102	ANEMIA – BLEEDING RELATED - MAJOR	A CONDITION IN WHICH RED BLOOD CELL COUNT AND/OR HEMOGLOBIN ARE LESS THAN NORMAL DUE TO BLOOD LOSS, AND THAT REQUIRES TREATMENT OR TRANSFUSION.
AE103	ANEMIA – BLEEDING RELATED - MINOR	A CONDITION IN WHICH RED BLOOD CELL COUNT AND/OR HEMOGLOBIN ARE LESS THAN NORMAL DUE TO BLOOD LOSS, AND THAT REQUIRES TREATMENT OR TRANSFUSION.
AE104	BLEEDING - CARDIOVASCULAR - MAJOR	ANY EPISODE OF MAJOR INTERNAL OR EXTERNAL BLEEDING THAT CAUSES DEATH, HOSPITALIZATION, OR PERMANENT INJURY (E.G., VISION LOSS) OR NECESSITATES TRANSFUSION. MAJOR BLEEDING UNEXPECTEDLY ASSOCIATED WITH MINOR TRAUMA SHOULD BE REPORTED AS A BLEEDING EVENT, BUT BLEEDING ASSOCIATED WITH MAJOR TRAUMA OR A MAJOR OPERATION (INCLUDING THE INDEX PROCEDURE) SHOULD NOT. THE LOCATION OF THE BLEEDING (GASTROINTESTINAL, GENITOURINARY, ETC.) MUST BE REPORTED. FOR EACH REPORTED BLEEDING EVENT, INDICATE IF SUBJECT IS TAKING ANTICOAGULANTS OR ANTI-PLATELET AGENTS.
AE105	BLEEDING - CARDIOVASCULAR - MINOR	"
AE106	BLEEDING - GENITOURINARY - MAJOR	"
AE107	BLEEDING - GENITOURINARY - MINOR	"
AE108	BLEEDING - GASTROINTESTINAL UPPER -MAJOR	"
AE109	BLEEDING - GASTROINTESTINAL UPPER -MINOR	"
AE110	BLEEDING - GASTROINTESTINAL LOWER -MAJOR	"
AE111	BLEEDING - GASTROINTESTINAL LOWER -MINOR	"
AE112	BLEEDING - MUSCULOSKELETAL/DERMATOLOGICAL -MAJOR	" (E.G. ECCHYMOSIS)
AE113	BLEEDING - MUSCULOSKELETAL/DERMATOLOGICAL -MINOR	" (E.G. ECCHYMOSIS)
AE114	BLEEDING - NEUROLOGICAL - MAJOR	" (E.G. CEREBRAL VASCULAR ACCIDENT)
AE115	BLEEDING - NEUROLOGICAL - MINOR	" (E.G. CEREBRAL VASCULAR ACCIDENT)
AE116	BLEEDING - PERIPHERAL VASCULAR -MAJOR	" (E.G. NOSEBLEEDS; HEMATOMAS)
AE117	BLEEDING - PERIPHERAL VASCULAR - MINOR	" (E.G. NOSEBLEEDS; HEMATOMAS)
AE118	BLEEDING - PULMONARY/RESPIRATORY - MAJOR	" (E.G. HEMOTHORAX)
AE119	BLEEDING - PULMONARY/RESPIRATORY MINOR	" (E.G. HEMOTHORAX)

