AE120	BLOOD SEPSIS	POSITIVE BLOOD CULTURE AND CLINICAL EVIDENCE OF INFECTION (E.G. FEVER, ELEVATED WBC COUNT, HYPOTENSION, END ORGAN DYSFUNCTION) EVENT MUST BE CONFIRMED BY 2 CONSECUTIVE POSITIVE BLOOD CULTURES, EXPLANT OR AUTOPSY.

Clinical Investigational Plan
 Protocol Number: 2010-03

AE CODE LIST	
CODE	DEFINITION
AE.1	BLOOD AND LYMPHATIC (INCLUDING ALL BLEEDING COMPLICATIONS) (CONTINUED)
AE122	PLASMA -FREE HEMOGLOBIN > 40 MG/DL ON TWO CONSECUTIVE MEASUREMENTS WITHIN 48 HOURS; OR CLINICAL DIAGNOSIS OF HEMOLYSIS EVIDENCED BY LABORATORY TESTING SUCH AS SERUM HEMOGLOBIN, HEMATOCRIT, AND/OR PLASMA-FREE HEMOGLOBIN (NOT IMMUNOLOGICALLY BASED)
AE123	DIFFUSE, NONSURGICAL, MICROVASCULAR HEMORRHAGE AND/OR THROMBOSES.
AE124	THROMBOCYTOPENIA (<150,000 PER CUBIC MILLIMETER), OR A RELATIVE DECREASE OF 50 PERCENT OR MORE FROM BASELINE, OR NEW THROMBOSIS IN A SUBJECT RECEIVING HEPARIN OR LMWH; CONFIRMED BY SEROLOGIC TESTING FOR PF4-HEPARIN ANTIBODIES.
AE125	THROMBOCYTOPENIA (<150,000 PER CUBIC MILLIMETER), OR A RELATIVE DECREASE OF 50 PERCENT OR MORE FROM BASELINE, ACCOMPANIED BY A LOW INDEX OF SUSPICION FOR HIT (I.E., NOT ASSOCIATED WITH HEPARIN USE, THE PRESENCE OF OTHER CAUSES OF THROMBOCYTOPENIA, SUCH AS DRUGS OTHER THAN HEPARIN, DIC OR OTHER CONSUMPTIVE PROCESSES, POST-TRANSFUSION PURPURA).
AE126	OTHER BLOOD OR LYMPHATIC EVENT THAT DOES NOT FIT IN ONE OF THE OTHER "BLOOD" CATEGORIES THAT REQUIRES HOSPITALIZATION OR MEDICAL INTERVENTION.
AE.2	CARDIOVASCULAR - ARRHYTHMIA
AE158	AN ABNORMAL HEARTBEAT IN WHICH THE HEART RHYTHM IS FAST AND IRREGULARLY IRREGULAR. EVENT SHOULD BE DOCUMENTED AND CONFIRMED BY ECG TEST RESULTS. AF IS CONSIDERED PERMANENT WHEN IT HAS PERSISTED BEYOND 1 YEAR AND ATTEMPTS AT CONVERSION HAVE FAILED OR COULD NOT BE ATTEMPTED.
AE149	ARRHYTHMIA - PERMANENT ATRIAL FIBRILLATION
AE157	AN ABNORMAL HEARTBEAT IN WHICH THE HEART RHYTHM IS FAST AND IRREGULARLY IRREGULAR. EVENT SHOULD BE DOCUMENTED AND CONFIRMED BY ECG TEST RESULTS. AF IS CONSIDERED PAROXYSMAL WHEN EPISODES OF AF TERMINATE SPONTANEOUSLY WITHIN 7 DAYS (MOST EPISODES LAST LESS THAN 24 HOURS)
AE141	ARRHYTHMIA - PAROXYSMAL ATRIAL FIBRILLATION (PAF)
AE142	ARRHYTHMIA - PERSISTENT ATRIAL FIBRILLATION
AE143	ARRHYTHMIA - ATRIAL FLUTTER
AE144	ARRHYTHMIA - PERSISTENT ATRIAL FIBRILLATION
AE145	ARRHYTHMIA - AV BLOCK - 1ST DEGREE
AE146	ARRHYTHMIA - AV BLOCK - 2ND DEGREE
AE147	ARRHYTHMIA - AV BLOCK - 3RD DEGREE

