		AORTIC: FLOW OBSTRUCTION OF THE AORTIC VALVE DUE TO RESTRICTED LEAFLET OPENING. THE SEVERITY IS CATEGORIZED AS: MILD - JET VELOCITY (M/S) <3.0; MEAN GRADIENT (MMHG) <25; VALVE AREA (CM2) >1.5.MODERATE - JET VELOCITY (M/S) 3.0-4.0; MEAN GRADIENT (MMHG) 25-40; VALVE AREA (CM2) 1.0- 1.5. OR SEVERE - JET VELOCITY (M/S) >4.0; MEAN GRADIENT (MMHG) >40; VALVE AREA (CM2) <1.0; VALVE AREA INDEX<0.6. MITRAL: MITRAL STENOSIS (MS) REFERS TO NARROWING OF THE MITRAL VALVE ORIFICE, RESULTING IN IMPEDANCE OF FILLING OF THE LEFT VENTRICLE IN DIASTOLE. THE SEVERITY OF MS IS CATEGORIZED AS: MILD - MEAN GRADIENT (MM HG) < 5, PULMONARY ARTERY SYSTOLIC PRESSURE (MM HG) < 30, VALVE AREA (CM2) >1.5. MODERATE - MEAN GRADIENT (MM HG) 5-10, PULMONARY ARTERY SYSTOLIC PRESSURE (MM HG) 30-50, VALVE AREA (CM2) 1.0-1.5. SEVERE - MEAN GRADIENT (MM HG) > 10, PULMONARY ARTERY SYSTOLIC PRESSURE (MM HG)> 50, VALVE AREA (CM2) <1.0. TRICUSPID: A NARROWING OF THE TRICUSPID VALVE OPENING THAT INCREASES RESISTANCE TO BLOOD FLOW FROM THE RIGHT ATRIUM TO THE RIGHT VENTRICLE. SEVERE TRICUSPID STENOSIS IS DEFINED AS A VALVE AREA LESS THAN 1.0 CM2.
AE220*	STENOSIS - AORTIC - MILD	"
AE221*	STENOSIS - AORTIC - MODERATE	"
AE222*	STENOSIS - AORTIC - SEVERE	"
AE223	STENOSIS - MITRAL- MILD	"
AE224	STENOSIS - MITRAL - MODERATE	"
AE225	STENOSIS - MITRAL - SEVERE	"
AE226	STENOSIS - PULMONARY- MILD	"
AE227	STENOSIS - PULMONARY - MODERATE	"
AE228	STENOSIS - PULMONARY - SEVERE	"
AE229	STENOSIS - TRICUSPID- MILD	"
AE230	STENOSIS - TRICUSPID- MODERATE	"
AE231	STENOSIS - TRICUSPID - SEVERE	"

AE CODE LIST	
CODE	DEFINITION
AE.6	
CARDIOVASCULAR - THROMBOEMBOLIC EVENT/VALVE THROMBOSIS
 
ANY EMBOLIC EVENT THAT OCCURS IN THE ABSENCE OF INFECTION AFTER THE IMMEDIATE PERIOPERATIVE PERIOD AND MAY BE MANIFESTED BY A NEUROLOGIC EVENT OR A NON-CEREBRAL EMBOLIC EVENT. EMBOLI CONSISTING OF NON-THROMBOTIC MATERIAL (E.G., ATHEROSCLEROSIS, MYXOMA) ARE NOT COUNTED.

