AE250	
THROMBOEMBOLIC EVENT – STROKE
 
INCLUDES ANY CENTRAL, NEW NEUROLOGIC DEFICIT, WHETHER TEMPORARY OR PERMANENT AND WHETHER FOCAL OR GLOBAL, THAT OCCURS AFTER THE SUBJECT EMERGES FROM ANESTHESIA. POSTOPERATIVE NEUROLOGIC SYMPTOMS THAT MIMIC THOSE OF A PREOPERATIVELY DOCUMENTED NEUROLOGIC EVENT AND THAT ARE CONFIRMED RADIOGRAPHICALLY TO BE CONSISTENT WITH THE FORMER EVENT ARE NOT COUNTED. CENTRAL NEUROLOGIC EVENTS THAT ARE CLEARLY RELATED TO AORTIC, INTERNAL CAROTID ARTERY, OR VERTEBRAL ARTERY DISEASE ARE ALSO NOT COUNTED. PSYCHOMOTOR DEFICITS FOUND BY SPECIALIZED TESTING ARE NOT CONSIDERED NEUROLOGIC EVENTS RELATED TO OPERATED VALVES. SUBJECTS WHO DO NOT AWAKEN OR WHO AWAKEN AFTER OPERATION WITH A NEW STROKE ARE NOT CONSIDERED TO HAVE SUSTAINED VALVE-RELATED NEUROLOGIC EVENTS. STROKE: A PROLONGED (>72 HOURS) OR PERMANENT NEUROLOGIC DEFICIT THAT IS USUALLY ASSOCIATED WITH ABNORMAL RESULTS OF MRI OR CT SCANS. SUBJECTS WITH MINIMAL, ATYPICAL, OR PROTEAN SYMPTOMS THAT LEAD TO RADIOGRAPHIC IMAGING DEMONSTRATING AN ACUTE ISCHEMIC EVENT ARE CONSIDERED TO HAVE SUSTAINED A STROKE. TIA: CHARACTERIZED BY FULLY REVERSIBLE SYMPTOMS OF SHORT DURATION. IF RADIOGRAPHIC IMAGING DEMONSTRATES AN ACUTE CENTRAL NEUROLOGIC LESION, HOWEVER, SUCH SUBJECTS ARE RECLASSIFIED AS HAVING SUSTAINED A STROKE.

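### Appendix 15.1 gives every minor bleeding code the same definition as its major counterpart, so the written text does not separate Major bleeding from All bleeding

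*Combined protocol and SAP*

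**What the plan says.** Section 7.3.1 names all bleeding and major bleeding as two separate safety endpoints and defines neither. Section 9.3 reports each as an early percentage (events within 30 days over enrolled subjects), a late linearized rate (later events over late subject-years) and a Kaplan-Meier estimate.

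The definitions are in Appendix 15.1, group AE.1:

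- AE104, the first major site code, reads "ANY EPISODE OF MAJOR INTERNAL OR EXTERNAL BLEEDING THAT CAUSES DEATH, HOSPITALIZATION, OR PERMANENT INJURY (E.G., VISION LOSS) OR NECESSITATES TRANSFUSION". It then covers trauma and surgery: bleeding unexpectedly associated with minor trauma is reported, "BUT BLEEDING ASSOCIATED WITH MAJOR TRAUMA OR A MAJOR OPERATION (INCLUDING THE INDEX PROCEDURE) SHOULD NOT".
- AE105, "BLEEDING - CARDIOVASCULAR - MINOR", has only a ditto mark in the definition column. So do the other seven minor site codes (AE107, 109, 111, 113, 115, 117, 119). Some rows add an example, but it is the same for both members of the pair.
- AE102 (bleeding-related anemia, major) and AE103 (the same, minor) each print "A CONDITION IN WHICH RED BLOOD CELL COUNT AND/OR HEMOGLOBIN ARE LESS THAN NORMAL DUE TO BLOOD LOSS, AND THAT REQUIRES TREATMENT OR TRANSFUSION".

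No other section grades bleeding. Section 11.4 describes the adjudication by the Clinical Events Committee (CEC) in terms of relatedness to the device or procedure. The Adverse Event form in Appendix 15.3 shows one class for all blood and bleeding events.

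**The concern.** The two endpoints differ only by grade, so the plan needs a rule that says when a bleed is major. AE104 supplies one: death, hospitalization, permanent injury or transfusion. The minor codes then repeat it, which leaves minor bleeding without a definition of its own. For the anemia pair the difficulty is sharper, because the minor code names transfusion and AE104 makes a transfused bleed major.

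At stake is what each rate counts. A site that follows the text cannot tell which code of a pair to use, and a reader of the report cannot tell which bleeds each rate contains. The trial's safety output is descriptive, so its value depends on clear definitions.

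**Working it through.** **1. Count the pairs.** AE102 to AE119 hold 1 anemia pair and 8 site pairs, so 1 + 8 = 9 minor codes: AE103, 105, 107, 109, 111, 113, 115, 117 and 119. In 9 of 9 the minor definition is the same as the major one. A conversion fault is unlikely: each minor site row has its own ditto mark, and AE103 is written out in full.

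**2. Apply the text literally.**

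| Bleed | Major site code | Minor site code |
|---|---|---|
| Meets an AE104 criterion | fits | fits (same text) |
| Meets none | does not fit | does not fit (same text) |

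What happens to a bleed in the second row depends on its features. Within AE.1 it could go to:

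- AE102 or AE103, if blood loss led to anemia needing treatment;
- AE123, if it was diffuse, nonsurgical and microvascular;
- AE126, "OTHER BLOOD OR LYMPHATIC EVENT THAT DOES NOT FIT IN ONE OF THE OTHER" blood categories, if it needed medical intervention.

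Otherwise it has no code in this group. None of these codes states a criterion for minor bleeding.

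**3. Compare shared text elsewhere in the appendix.** The aortic stenosis codes also share one text, but that text sets limits: "THE SEVERITY IS CATEGORIZED AS: MILD - JET VELOCITY (M/S) <3.0; MEAN GRADIENT (MMHG) <25", with further limits for moderate and severe. The stroke and TIA codes share a text that separates them by duration and imaging, for example "TIA: CHARACTERIZED BY FULLY REVERSIBLE SYMPTOMS OF SHORT DURATION". The bleeding text has no such sentence.

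**4. Check the anemia pair against AE104.** The group heading begins "BLOOD AND LYMPHATIC (INCLUDING ALL BLEEDING COMPLICATIONS", which hints that the anemia codes feed the bleeding endpoints, but no section says so. If they do, a transfused bleed could be coded minor under AE103. A treated, untransfused one could be coded major under AE102, which also lacks AE104's exclusion of bleeding from the index operation.

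**5. Size of one reclassified event.** The plan gives no expected bleeding rate to reproduce. Inputs: up to 200 subjects (section 9.1), 5 years of follow-up (section 7), late period after day 30 (section 9.3).

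- Early: 1/200 = 0.5 percentage points, and more if fewer than 200 are enrolled.
- Late, everyone followed for 5 years (assumption): 200 × (5 − 30/365.25) = 983.6 subject-years, and 1/983.6 = 0.10% per year.
- Late, half that exposure (assumption): 1/491.8 = 0.20% per year.

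These are effects per event. The documents do not say how many bleeds would be affected.

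**The case against.** The strongest reply is that the table has a label column as well as a definition column. AE104 opens by restricting itself to major bleeding and lists four criteria, so major bleeding is defined, and minor is naturally the remainder. The dittos may serve only to carry down instructions that apply to every bleed, such as recording location and anticoagulant use. Minor codes with ecchymosis or nosebleeds as examples suggest that lesser bleeds were meant to have a place. Nor is the contrast with stenosis uniform: the pulmonary stenosis grades, and the mild and moderate tricuspid grades, also rely on their labels without limits of their own.

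Much of this stands. The remainder reading is the natural one, and the endpoints can be tabulated by assigned code. But the rule is not written, the paired major codes carry the same examples, and AE103 does not fit the remainder reading because it names transfusion. The ungraded stenosis codes show a similar gap, not a cure.

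There is also real mitigation. The CEC reviews endpoint-related events with source documents and records its rulings, and the Adverse Event form captures death, hospitalization, permanent impairment and transfusion. Neither becomes a grading rule until the plan says so.

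A reader might infer more than the documents support:

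- **That every lesser bleed ends in AE126 and drops out of all bleeding.** AE102, AE103 and AE123 are other possible destinations.
- **That the site codes inflate the major rate.** A bleed that fails AE104 has no textual route to a major site code. The miscoding the text permits there is an AE104-level bleed recorded as minor, which lowers the major rate. Only the anemia pair, if it counts, could act in both directions.
- **That a total shift can be quoted.** No bleed counts are given.

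**Conclusion.** The definitions in Appendix 15.1 do not separate major from minor bleeding in any of the 9 pairs, and for the anemia pair the minor text conflicts with AE104. This is an error in a stated definition affecting two named endpoints, and it should be fixed. It does not threaten a trial decision, because the rates are descriptive and no limit is tested.

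Each affected event is worth at least 0.5 percentage points on the early rate. On the late rate it is worth about 0.10% per year if all 200 subjects complete follow-up, or 0.20% at half that exposure. The total effect cannot be estimated.

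The duplication itself is certain from the text. How sites code in practice is not: section 12.9.2 promises Case Report Form Instructions, which are not among the documents and may hold a grading rule. The finding concerns the appendix as written.

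**What to change.** 1. **Minor site codes.** Define each of the 8 as bleeding at that site that does not meet the AE104 major criteria, and state that AE104's exclusions apply to both grades.
2. **Anemia pair.** Change AE102 and AE103 together and keep the blood-loss anemia content: major if the AE104 criteria are met, minor if not. Changing only one would leave an overlap. State whether these codes count toward the bleeding endpoints; if they do, count an episode recorded under both an anemia code and a site code once.
3. **Analysis rule.** Derive major status for every reported bleed from the Adverse Event form fields for death, hospitalization, permanent impairment (the nearest field to permanent injury) and transfusion. State whether a prolonged stay counts as hospitalization, since the seriousness item merges the two while the intervention items separate them. Refer unclear cases to the CEC, and add that task to section 11.4, whose stated adjudication is relatedness.

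**Cost.** Section 15 allows appendices to be updated independently, and no new form field is needed. The work is rewording 10 definitions (8 site codes plus AE102 and AE103), one statement on the anemia codes, one analysis rule and some case review, including any bleeds already recorded in the 20 subjects implanted under Version A. The reported major-bleeding rate may change. A minor bleed that a site never reported cannot be recovered this way.
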